3.1.2 Expected Duration of the Study

The anticipated enrollment period will be 2 years. The total anticipated study period will be 2.5 years.

3.2 Primary Study Endpoints

The primary endpoint that will be evaluated at the end of the study includes:

3.2.1 Investigator Engagement: Investigator engagement will be assessed at the study site level as well as across all study sites.

Investigator engagement will be assessed through the number of data updates delivered by the μCor subject management system, the time spent reviewing each data report, the number of medication changes based on μCor data, the number of lifestyle modifications that are recommended to the subject, the number of medication changes based on symptoms reported by subjects or from subject incidental findings, and the number of times high μCor measurements are reduced below threshold levels after medication was titrated or lifestyle modifications were recommended.

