Unplanned visits to the physician office or hospital will be captured and defined as visits that the subject did not plan beyond 48 hours. In case of adverse skin reaction to the μ Cor adhesive and/or electrodes, on the discretion of physician, subjects may discontinue wearing the device for up to 48 hours. In the event the subject has stopped wearing the device completely, follow up phone calls will continue to be conducted per protocol in order to capture clinical information.

During the Day 90 visit, the subject will be given the option to continue wearing the μ Cor for an additional 90 days. Furthermore, if the subject experienced a heart failure related clinical event within the initial 90 days of wear, the subject will be given the option of wearing the μ Cor for 30 days following the heart failure event. If the subject chooses additional wear time, weekly phone calls and monthly visits will be structured identical to that of the main study period. The μ Cor will be returned at end of use.

Data updates will be delivered to the site when the day averaged TFI exceeds a threshold greater than three standard deviations of the baseline TFI level for three consecutive days. Upon receiving a device data update, the investigator will receive detailed information into how the device measurements have tracked over the days leading up to the notification. When receiving a data update, the site will be required to review the most recent report within 24 hours, and explain their reasoning whether they choose to contact the subject or not to contact the subject. The data review must occur prior to every scheduled subject contact.

When acting upon the data update, the site may contact the subject to assess the subject's current symptoms and history, and make an informed decision within the context of both device measurements and standard medical care as to what actions to take with the subject. Potential actions the site could take will include, a prescription drug change or titration, a request for an office visit, a request for hospitalization, and request for lifestyle or diet modifications. The site will document any changes to subject care within the case report forms. Unscheduled contacts that the subject initiates will be recorded as well.

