 - Any physician visits, both planned and unplanned
 - Any hospitalization, including heart failure hospitalization
 - Any emergency room visits
 - Any symptoms, including syncope, dyspnea, palpitations and chest pain
- 6.2.4.4 A weight measurement will be obtained.
- 6.2.4.5 Subjects will be given a physical assessment
- 6.2.2.6 Daily cardiac medications taken by the subject will be reviewed and compared to the last listed cardiac medications documented by the study. Any new cardiac medications or changes in medication will be recorded (i.e. dosage changes or new medications administered)
- 6.2.4.7 Subjects will be asked if they would like to continue wear for an additional 90 days. If the subject had experienced a heart failure related clinical event within the previous 90 days, the subject will also be given the option to continue wear for 30 days following the most recent heart failure event.

6.3 *Unscheduled Visits*

- 6.3.1 Clinic visits, ED visits, and hospitalizations that have resulted from a device data update will be defined as unscheduled events. Separately, all heart failure related contact with the subject either initiated by the subject or the site will be defined as an unscheduled visit. Heart failure contact includes, but is not limited to, contact with the subject concerning new or worsening heart failure symptoms such as dyspnea, pedal edema, and shortness of breath.
- 6.3.2 Upon receiving a data update, which will be initiated when the day averaged TFI readings have exceeded for three consecutive days a threshold defined by three standard deviations of baseline TFI, the site study team will reach out to the subject within 24 hours. The data update will be delivered to the site via either fax, email, or phone call.
- 6.3.3 The investigator will make a decision whether to contact the subject or take no further action based on the data update, and document the reason. There will be a structured interview between the investigator and subject. The investigator will have access to a report that displays the device data.
- 6.3.4 If the subject is called after device data update, the subject's symptoms and recent history will be documented, and a medical decision, within the context of standard of care,

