will be given to the patient. The medical decision may include assessment with no action required, adjusting or starting new medication, requesting an office visit, requesting an ED visit, requesting a lifestyle/diet change, requesting a hospital admission, or no change at all. All decisions will be documented.

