8.3 Endpoint Assessment

8.3.1 Primary endpoint

The primary endpoint will be assessed in an observational nature through the frequency and characterization of site engagement with uCor data. The assessment will be made study-wide in addition to geographic regions. Site engagement will be assessed through the following:

- 8.3.1.1 The number of data updates received by the µCor subject management system.
- 8.3.1.2 An assessment of the approximate time spent reviewing data reports assessed within sites and across sites. Investigators will be asked, for each report, whether they spent 0-5min, 5-10min, or greater than 10 minutes reviewing the data.
- 8.3.1.3 The number of medication changes based on µCor data and the number of lifestyle modifications were recommended to the subject.
- 8.3.1.4 The number of medication changes based on symptoms reported by subjects or from subject incidental findings.
- 8.3.1.5 The number of times high µCor measurements were reduced below threshold levels after medication was titrated or lifestyle modifications were recommended.

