8.4 Statistical Methods

Concerning the primary endpoint, investigator engagement will be assessed through the number of data updates delivered by the µCor subject management system, frequency of medication changes based on µCor data, frequency of lifestyle modifications that are recommended to the subject, frequency of medication changes based on symptoms reported by subjects or from subject incidental findings, and frequency high µCor measurements that are reduced below threshold levels after medication was titrated or lifestyle modifications were recommended.

Concerning the secondary endpoints, associations between µCor measurements and clinically related heart failure events will be assessed through sensitivity/specificity analyses. µCor measurements at both baseline (first day of fitting) and the time of heart failure admission will be compared among subjects with or without heart failure related events using t-tests or other appropriate statistical methods.

For primary, secondary, and safety endpoints, descriptive statistics and qualitative analysis will be performed as appropriate. Descriptive statistics will include frequency of data updates delivered by the µCor data system, frequency of physician action to µCor data or µCor data updates, and physician action events as a percentage of all data updates received.

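### The first-listed primary engagement measure counts device-triggered updates, which is exposure; the per-update response that would show engagement is left undefined in 8.4 and missing from 3.2.1 and 8.3.1

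*Combined protocol and SAP*

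**What the plan says.** Section 2.1 gives one primary objective, investigator engagement with the device data. Section 3.2.1 makes it the primary endpoint, to be assessed at each site and across sites. The number of data updates comes first in all three places that list the measures: 3.2.1 ("Investigator engagement will be assessed through the number of data updates delivered by the" system), 8.3.1.1 ("The number of data updates received by the" system) and the first paragraph of 8.4.

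Section 3.1.1 says what produces an update: "Data updates will be delivered to the site when the day averaged TFI exceeds a threshold" of more than three baseline standard deviations, three days running. Section 6.3.2 repeats the trigger.

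The protocol also says what the site must do next. Under 3.1.1, "the site will be required to review the most recent report within 24 hours", and it must "explain their reasoning whether they choose to contact the subject or not to contact the subject". Under 6.3.3 the investigator makes a "decision whether to contact the subject or take no further action based on the data update, and document the reason". Section 6.3.4, on calls made after an update, adds: "All decisions will be documented".

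For all endpoints, the last paragraph of 8.4 promises descriptive statistics that include "physician action events as a percentage of all data updates received".

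**The concern.** A count of updates is fixed by the subject's readings and the threshold. The site has no part in triggering one, and treatment that works could lower the count. Listed as a measure of engagement and reported by site, it describes how often a site had something to respond to, not whether it responded.

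The responses closest to engagement are a timely review of the report and a reasoned decision to contact or not. The protocol requires both, but none of the lists in 3.2.1, 8.3.1 and 8.4 names either. The one per-update response rate, in 8.4, is not carried into the endpoint definition and does not say what counts as an action.

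What is at stake is interpretation. The study is descriptive, so its primary result is only as good as the meaning of its measures. If counts are tabulated by site or region as engagement, differences in case mix, wear and enrolment can be read as differences in investigator behaviour.

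**Working it through.** The plan has no figure to reproduce here. Section 8.1 gives 80 sites and 300 subjects without alpha, power, precision target or expected number of updates. The only arithmetic available is 300/80 = 3.75 subjects per site, which lies within the stated three to five. The check is therefore mainly a comparison of sections.

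**1. What the six measures in 3.2.1 describe**

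| Measure | What it describes |
|---|---|
| Data updates | System output, triggered by subject TFI |
| Review time per report | Investigator behaviour |
| Medication changes based on device data | Investigator behaviour |
| Lifestyle recommendations | Investigator behaviour |
| Medication changes based on symptoms or incidental findings | Investigator behaviour |
| High readings falling below threshold after action | Subject response |

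Four are behaviours, one is a system output and one is a subject response. None is the share of updates reviewed within 24 hours, and none is the contact decision. The primary-endpoint paragraph of 8.4 also drops review time, leaving five.

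**2. How far the count moves with no change in behaviour**

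Expected count at a site = (subjects) × (wear days per subject) × (updates per wear day). None of the three factors is an act of reviewing or responding. With the last two equal, 8.1's range of three to five subjects gives 5/3 = 1.67. The plan specifies no rate per subject or per wear day. If updates also continue and are counted during the optional second 90 days (the plan does not say), a subject who takes it up contributes (90 + 90)/90 = 2 times the exposure.

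**3. Whether the other measures separate a considered response from none**

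Assume two sites with 10 updates each. Site A ignores all of them. Site B reviews each in under five minutes and documents a reasoned decision not to contact. Read *physician action* as a change in care.

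| Quantity | Site A | Site B |
|---|---|---|
| Update count | 10 | 10 |
| Device-based medication or lifestyle changes | 0 | 0 |
| Action percentage (8.4) | 0/10 = 0% | 0/10 = 0% |
| Review time (8.3.1.2) | Blank or 0-5 min | 0-5 min |
| Share with documented decision and reason | 0/10 = 0% | 10/10 = 100% |

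The review-time item asks for 0-5, 5-10 or more than 10 minutes. The lowest category starts at zero and there is no category for a report that was not reviewed, so it does not reliably separate the two sites. Only the last row does, and it is not a listed measure.

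**4. The numerator of the 8.4 percentage**

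Section 8.4 speaks of action on device data as well as on updates, and 6.6 allows changes in care after the routine weekly review. Actions that no update prompted could therefore enter a numerator whose denominator is updates. Section 6.3.4 also lists outcomes in which nothing changes, so it is unclear whether these count as actions.

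**5. What is recorded**

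Section 6.3.3 requires the contact decision and its reason to be documented. No section says that the date and time of the review are recorded. Section 3.1.1 ties 24 hours to reviewing the report, 6.3.2 ties it to reaching out to the subject, and 6.3.3 leaves contact to a decision. A timeliness measure cannot be defined until these agree.

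**6. Whether an added share would be estimable**

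Let A be the total updates, p the share and ICC the within-site correlation. All three are assumed, because the documents give none. Updates are taken as spread evenly over 80 sites.

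Half-width of a 95% interval = 1.96 × √[p(1−p) × D/A], with D = 1 + (A/80 − 1) × ICC.

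Worked case: A = 300, p = 0.5, ICC = 0.3 gives D = 1 + 2.75 × 0.3 = 1.825 and a half-width of 1.96 × √(0.25 × 1.825/300) = 0.076.

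Over p = 0.5 to 0.8 and ICC = 0 to 0.3:

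| A | Half-width, percentage points |
|---|---|
| 100 | 7.8 to 10.2 |
| 300 | 4.5 to 7.6 |
| 600 | 3.2 to 6.9 |

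That is adequate for a descriptive study-wide estimate.

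**The case against.** The strongest reply is that the endpoint is mostly behavioural already. Four of six measures are things investigators do, review time is asked for every report, and 8.4 gives a per-update action rate that applies to the primary endpoint. The update count has to be reported anyway as the denominator. This stands, and it limits the point to how the count is labelled and what the rate means.

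Three stronger readings are tempting, and the documents do not support them.

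- A reader might infer that the study could report high engagement with no evidence that anyone looked at the data. Review time per report is direct evidence on that, even though it is self-reported and lacks a category for no review.
- A reader might infer that sites with sicker subjects would score as more engaged. Section 8.3.1 describes frequency and characterisation only, with no composite, ranking or threshold, so nothing is scored. The trigger is relative to baseline TFI, so it reflects change and not severity as such. A site that ignored every update would show no update-prompted actions beside its count.
- A reader might infer that review within 24 hours is already recorded and merely left unused. The protocol requires it, but no section says its time is captured.

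It can also be argued that the proposed shares measure adherence to mandatory steps and may sit near 100%. That is possible. A share near 100% would still be informative, since it would show that few updates went unanswered, which the present measures cannot show reliably.

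**Conclusion.** The point holds in a limited form. The update count is exposure and should not be listed as a measure of engagement. The per-update action percentage that would put it to proper use is missing from 3.2.1 and 8.3.1 and has no defined numerator. As a result, a considered decision not to contact may be indistinguishable from no response.

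The size is modest. One of six listed measures is misclassified, site counts can differ 1.67-fold from enrolment alone within the planned range (assuming equal update rates and wear), and no test, power or sample-size statement changes. The conclusion about indistinguishable sites assumes that *physician action* means a change in care; a definition that included documented decisions would remove it. The change is worth making because engagement is the only primary objective and most of the data needed are already required.

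**What to change.** 1. In 3.2.1, 8.3.1.1 and 8.4, report the number of updates as the denominator (exposure) and no longer as a measure of engagement.
2. Carry the per-update action percentage from 8.4 into 3.2.1 and 8.3.1. Define *physician action*, state whether a contact or a documented decision not to contact counts, and limit the numerator to responses to updates. Report actions arising from weekly reviews separately.
3. Add as a primary measure the share of updates with a documented contact or no-contact decision and its reason, by site, by region and study-wide.
4. Add the share of updates reviewed within 24 hours only if a review timestamp is captured, and only after 3.1.1 and 6.3.2 have been reconciled on what must happen within 24 hours.

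Items 1 to 3 cost wording only, because 6.3.3 already requires the decision and reason to be documented. Item 4 costs one field on the update form, plus the reconciliation, which is needed in any case.

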3.3 Secondary Study Endpoints

The various secondary endpoints that will be evaluated during the entire study include:

3.3.1 Correlation between μ Cor measurements and clinically related heart failure events.

3.3.2 Correlation between μ Cor measurements and subject reported symptoms.

3.3.3 Hospital readmission rate, physician visit rate, and outpatient clinic visit rate during the study period.

3.3.4 Mortality, heart failure related events, quality of life (QoL), and health care utilization data at 6 months and one year post enrollment.

3.4 Safety Endpoints

3.4.1 The number and severity of all adverse events that are causally related to the μ Cor system or study specific procedure.

4 Study Subject

4.1 Inclusion Criteria

The following criteria will be used to include subjects in the study: An acute heart failure event requiring medical management is defined in section 6.1.3. The index hospitalization and six month prior event must have started two weeks apart from one another.

4.1.1 Subjects hospitalized for acute decompensated heart failure and enrolled in the study within 10 days post-hospital discharge.

4.1.2 Subjects who have had an acute heart failure event requiring medical management in the previous 180 days of index hospitalization admission. This acute heart failure event admission must be at least 2 weeks apart from the event admission in 4.1.1

4.1.3 Subjects 21 years of age or older on the day of screening.

4.2 Exclusion Criteria

The following criteria will be used to exclude subjects from the study:

4.2.1 Subjects who are wearing the wearable cardioverter defibrillator (WCD)

4.2.2 Subjects not expected to survive one year from enrollment from non-cardiac disease.

4.2.3 Subjects with skin allergy or sensitivity to medical adhesives.

4.2.4 Subjects anticipated to start dialysis within 90 days.

- 4.2.5 Subjects currently implanted with an S-ICD system.
- 4.2.6 Subjects who received a percutaneous coronary intervention (PCI) less than 24 hours after onset of heart failure related symptoms during index hospitalization.
- 4.2.7 Subjects who are unable to participate in all follow up visits.
- 4.2.8 Subjects participating in research other than a non-interventional registry at the time of enrollment.
- 4.2.9 Subjects currently implanted with an LVAD.
- 4.2.10 Subjects with self-reported pregnancy.
- 4.2.11 Subjects currently being actively managed with any device based remote HF monitoring.

5 Study Enrollment Plan

5.1 Enrollment Strategy

Patient enrollment strategies may be targeted at both the investigator and the patient as a way to engage all interested parties and provide information materials for the study. Strategies may include patient and/or investigator focus groups, educational lectures, web sites, flyers, or brochures to assist in the recruitment and screening process, if needed. Any patient facing materials will be submitted for approval to the IRB.

5.2 Study Size

A total of 300 subjects.

5.3 Enrollment Period

The anticipated total enrollment period for this study is 2 year, with a total anticipated study period would be 2.5 years.

5.3.1 Data Usage, Informed Consent and Reflection Period

All subjects will be informed about the use of their data in the clinical study according to the requirements of data privacy regulations, i.e. consent to processing medical data of the subject to a central scientific database. Sufficient time will be allowed for data usage information to be read and for questions to be asked during the informed consent process. The subjects will be informed that withdrawal of their consent in the clinical study is possible at any time and that a withdrawal is possible without stating a reason, is conducted without prejudice, and does not place the subject at any disadvantage in the study. The subject will receive detailed training on the use of the device by the site researcher. This will give the subject the opportunity to raise further questions about the device and data handling to the responsible physician.

5.4 Early Withdrawal of Subjects

5.4.1 When and How to Withdraw Subjects

All patients enrolled into the study can withdraw at any time regardless of the reason for withdrawal. Patients may withdraw consent for use of data and exit the study at any time without prejudice to further treatment.

5.4.2 Data Collection and Follow-up for Withdrawn Subjects

Reason for subject withdrawal from the study, if known, will be documented and all study data will be retained for data analysis. All possible attempts should be made to obtain follow up data at the end of study without contacting the subject. Only in the case of specific withdrawal of consent of use of data will the subject's data be deleted from the database (if possible).

6 Study Procedures

6.1 Subject Recruitment, Subject Screening, and Definitions

6.1.1 Subject recruitment

Subjects will be identified from chart review. Subjects may be recruited in both inpatient and outpatient settings. The investigator will discuss the details of the clinical study including benefits and risks of participating in the study prior to enrollment.

6.1.2 Subject screening

Subject chart review will take place based on the inclusion/exclusion criteria.

6.1.3 Definitions

An acute heart failure event requiring medical management, and a heart failure related clinical event, is defined as a hospitalization, emergency room visit, observation unit visit, or unplanned clinic visit where medical management or treatment for HF related pulmonary congestion is administered.

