2.2 Secondary Objective(s)

The specific secondary objectives that will be evaluated during the entire study include:

2.2.1 To identify correlations between μ Cor measurements (physiologic variables including thoracic impedance, cardiac rhythm, respiration rate) and heart failure related clinical events. A heart failure related clinical event is defined in section 6.1.3.

2.2.2 To identify correlations between μ Cor measurements (physiologic variables including thoracic impedance, cardiac rhythm, respiration rate) and patient reported symptoms.

2.2.3 To identify the hospital readmission rate, physician visit rate, and outpatient clinic visit rate of subjects during the study period.

2.2.4 To identify the mortality rate, cause of death, quality of life (QoL), and health care utilization among patients six months and one year after enrollment into the study.

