6.4 Long-term Clinical Outcome Assessment

The subject will receive a follow up phone call 6 months (180 days) and 1 year (365 days) from the enrollment date to assess for mortality status, heart failure related clinical events that have occurred since the end of μCor wear, and any health care utilization that has occurred since the end of μCor wear. A chart review will be performed during both of these calls as well. Subjects will answer mailed heart failure questionnaires and mail the questionnaires back to the site. These follow-up calls must occur within +/- 2 weeks of the scheduled call.

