8.3.2 Secondary endpoints

- 8.3.2.1 Strength of association between µCor measurements and clinically related heart failure events.
- 8.3.2.2 Strength of association between µCor measurements and subject reported symptoms.
- 8.3.2.3 Descriptive statistics around hospital readmission rate, physician visit rate, and outpatient clinic visit rate during the study period.
- 8.3.2.4 Descriptive statistics around mortality, heart failure related events, quality of life (QoL), and health care utilization data at 6 months and on year post enrollment.

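### Heart failure death is outside the event definition that sorts subjects in 8.4, and no endpoint, procedure or analysis item specifies the cause of death named in objective 2.2.4

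*Combined protocol and SAP*

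**What the plan says.** **Event definition.** Section 6.1.3 gives one definition for both the qualifying acute event and the heart failure related clinical event: "a hospitalization, emergency room visit, observation unit visit, or unplanned clinic visit where medical management or treatment" for heart failure related pulmonary congestion is given. It is a closed list of four kinds of treated visit.

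**Use in the analysis.** Under section 8.4, associations between device measurements and "clinically related heart failure events will be assessed through sensitivity/specificity analyses". Measurements at baseline and at heart failure admission "will be compared among subjects with or without heart failure related events using t-tests or other appropriate statistical methods". Nothing says whether a subject who dies is an event, a competing event, censored or excluded. Section 8.6.1 does not list death among the sources of missing data, and 8.6.3.1 only rules out replacing missing values.

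**Cause of death.** Objective 2.2.4 is "To identify the mortality rate, cause of death, quality of life (QoL), and health care utilization among patients" at six months and one year. The matching endpoint, 3.3.4, reads "Mortality, heart failure related events, quality of life (QoL), and health care utilization data at 6 months and one year post enrollment". Analysis item 8.3.2.4 promises "Descriptive statistics around mortality, heart failure related events, quality of life (QoL), and health care utilization data" at the same times. The calls in section 6.4 are made "to assess for mortality status, heart failure related clinical events that have occurred since the end of" device wear, together with a chart review. Section 3.1.1 refers to mortality data without saying what they contain, the Study Summary speaks of vital status, and Table 1 has no row for death.

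**The concern.** The device-accuracy question (endpoint 3.3.1, item 8.3.2.1) depends on putting subjects in the right group. Take a subject who dies of heart failure outside hospital with no treated visit. The definition leaves that subject without an event. If the fluid index had risen and a data update had gone out, a correct warning would be counted as a false alarm. If the device had stayed silent, a missed death would be counted as a correct negative and would not enter the sensitivity denominator. Either way the most severe heart failure outcome is treated as a non-event.

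Cause of death is what would allow these subjects to be identified, and it is an objective in its own right. Yet the step from objective to endpoint, procedure and analysis drops it. The other data streams do not clearly supply it. Visits and weekly calls ask the subject about events. Section 10 covers device effects and events arising from changes in care prompted by device data, so an ordinary heart failure death has no explicit adverse event record.

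**Working it through.** **What can be reproduced.** The plan gives no death rate, event rate, effect size or power. Its only planning figures are 300 subjects, 80 sites and 3 to 5 subjects per site; 300/80 = 3.75, which is consistent. No stated figure is contradicted.

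**Illustration.** Only N = 300 comes from the documents. Assumed:

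- E = 45, 75 or 105 subjects with a treated-visit event;
- D = 3 to 15 heart failure deaths without one;
- true sensitivity 70%, true specificity 80%;
- the D subjects alert at the sensitivity rate, so 30% of them have no alert, and their mean equals that of the event group;
- one classification per subject over the whole wear period.

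With the D subjects left in the group without events:

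- Observed specificity = [0.80 × (300 − E − D) + 0.30 × D] / (300 − E), a shortfall of 0.50 × D / (300 − E).
- Share of the true mean difference retained = 1 − D / (300 − E).
- Power for an assumed true difference of 0.4 SD (two-sided 0.05, normal approximation, SD held at 1) = Φ(difference/SE − 1.96), with SE = √(1/n₁ + 1/n₂). Group sizes are E and 300 − E as misclassified, and E + D and 300 − E − D with the deaths counted as events.

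| E | D | Observed specificity | Difference retained | Power, misclassified | Power, deaths counted |
|---|---|---|---|---|---|
| 45 | 3 | 79.4% | 98.8% | 68.6% | 71.9% |
| 45 | 15 | 77.1% | 94.1% | 64.4% | 79.1% |
| 75 | 6 | 78.7% | 97.3% | 83.1% | 86.8% |
| 105 | 3 | 79.2% | 98.5% | 90.2% | 91.4% |
| 105 | 15 | 76.2% | 92.3% | 86.2% | 92.4% |

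Worked case, E = 75 and D = 6: (0.80 × 219 + 0.30 × 6) / 225 = 177/225 = 78.7%; retained difference 1 − 6/225 = 97.3%. The power gap combines the diluted difference with the smaller event group.

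**If the device misses these deaths.** Suppose instead that the D subjects alert only at the false-positive rate, 1 − 0.80 = 20%. Specificity is then unaffected, but sensitivity is overstated. At E = 75 and D = 6 the plan would report 70%, whereas with the deaths counted it is (0.70 × 75 + 0.20 × 6) / 81 = 53.7/81 = 66.3%. The direction of the error therefore depends on whether the device alerted, and the plan does not separate the two cases.

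**The case against.** **The plan is silent rather than wrong.** Section 8.4 never says that a death is scored as no event. It allows other appropriate methods and gives neither a unit of analysis nor a time window for sensitivity and specificity, so such subjects could be excluded or censored. It stands that the classification follows from reading two sections together. But a closed definition combined with a two-way split puts these subjects in the group without events unless a rule is added. If one is added only after the data are seen, that is a weakness too.

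**The definition suits the device.** It is tied to treated pulmonary congestion, which is close to what a thoracic fluid monitor measures, and it also serves eligibility under 4.1.2, where death cannot be a component. Both points stand. They are reasons to confine the change to 8.4 and to keep the treated-visit analysis alongside.

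**Stronger readings that the documents do not support.** A reader might infer that cause of death will never be collected and that misclassified subjects cannot be recovered. Section 3.1.1 calls for mortality data, 6.4 requires a chart review at both long-term contacts, 12.2.1 lists hospital records and charts as source documents, and the case report forms are not in the documents. Cause may therefore be captured. What stands is that no item, source or classification is specified, the first such review is at 180 days, and a site's chart tells least about deaths outside hospital. A reader might also infer that section 10 excludes every death. It does not: 10.1 includes adverse events related to medication changes and procedures initiated by device data.

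**Conclusion.** The point holds as a mismatch within the plan. Section 8.4 classifies by a definition that omits death and has no rule for it, and one component of objective 2.2.4 has no specified data item or analysis. Neither statement needs a numerical assumption.

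The size does. Over the assumed range, specificity is 0.6 to 3.8 points too low (1.5/255 to 7.5/195) and the mean difference 1% to 8% too small (3/255 to 15/195). That is modest unless untreated heart failure deaths are numerous relative to events. A reader might multiply 300 by an assumed 5% to 15% mortality and an assumed 20% to 30% without a treated visit, and take the resulting 3 to 13.5 subjects as the number misclassified. That counts deaths from any cause. With an assumed heart failure share of 30% to 60% it becomes 0.9 to 8.1, so D = 15 is an extreme case.

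The secondary association analyses and objective 2.2.4 are affected. The primary engagement endpoint is not.

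**What to change.** 1. Record date of death, cause (heart failure, other cardiovascular, non-cardiovascular, unknown) and source of the information, from the chart review already planned in 6.4 and at any notification of a death, including during the weekly calls.
2. Name cause of death in 3.3.4, 6.4 and 8.3.2.4, with a matching row in Table 1.
3. For the 8.4 analyses only, count a heart failure death during wear as an event. Leave 6.1.3 unchanged for eligibility.
4. Follow subjects who die of other causes only to the date of death. This requires 8.4 to state the unit and time window of the sensitivity and specificity analysis.
5. Report a sensitivity analysis using the treated-visit definition alone.

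The cost is a few case report form fields and some sentences in the protocol; no clinical care changes. The downside is that some causes will be coded unknown, so 8.4 should say in advance how those deaths are counted.
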